# 5. TREATMENT OF SUBJECTS

This chapter is only applicable for intervention studies:

Not applicable

# 5.1 Investigational product/treatment

Not applicable

# 5.2 Use of co-intervention (if applicable)

Not applicable

# 5.3 Escape medication (if applicable)

# 6. INVESTIGATIONAL PRODUCT

- 6.1 Name and description of investigational product(s)
- 6.2 Summary of findings from non-clinical studies
- 6.3 Summary of findings from clinical studies
- 6.4 Summary of known and potential risks and benefits
- 6.5 Description and justification of route of administration and dosage
- 6.6 Dosages, dosage modifications and method of administration
- 6.7 Preparation and labelling of Investigational Medicinal Product
- 6.8 Drug accountability

# 7. NON-INVESTIGATIONAL PRODUCT

- 7.1 Name and description of non-investigational product(s)
- 7.2 Summary of findings from non-clinical studies
- 7.3 Summary of findings from clinical studies
- 7.4 Summary of known and potential risks and benefits
- 7.5 Description and justification of route of administration and dosage
- 7.6 Dosages, dosage modifications and method of administration
- 7.7 Preparation and labelling of Non Investigational Medicinal Product
- 7.8 Drug accountability

#### 8. METHODS

# 8.1 Study parameters/endpoints

# 8.1.1 Main study parameter/endpoint

Main study parameters are the SRS-A score, the ASQ and ECR-R.

The *Social Responsiveness Scale – Adult version* (SRS-A) (Constantino, 2005; Dutch translation: Noens et al., 2012), a screening tool for identifying possible ASD characteristics in adults suspicious for ASD, is 64-item self-report questionnaire measuring various dimensions of interpersonal behavior, communication, and rigid, repetitive behaviour and interests, characteristic for adults with ASD. Each item is rated on a 1-4 point scale. The SRS-A showed average to good internal consistency and test-retest reliability, adequate content validity, and good congruent validity (Noens et al., 2012). The Cronbach's alpha for the SRS-A scales were for Social awareness .80, Social communication .82, Social motivation .81, and Restricted interests & repetitive behavior .81 (Bezemer et al., 2020).

The Attachment Styles Questionnaire (ASQ; Mosterman & Hofstra, 2015), translation of the Dutch Hechtingsstijllijst (HSL) (Oudenhoven et al., 2003), is a questionnaire consisting of 24 items based on four vignettes (Bartholomew & Horowitz, 1991) and the Relationship Scales Questionnaire (RSQ; Griffin & Bartholomew, 1994). The ASQ assesses four attachment styles (secure, preoccupied, fearful, and dismissing). The 5-point rating scale ranges from 1 (*strongly disagree*) to 5 (*strongly agree*). The internal consistencies (Cronbach's alpha) were 0.75 for the secure style, 0.80 for the preoccupied style, 0.79 for the fearful style, and 0.62 for the dismissing style (Mosterman & Hofstra, 2015).

The Experiences in Close Relationships Questionnaire Revised (ECR-R) (Fraley, Waller, & Brennan, 2000; Dutch translation by Conradi et al., 2006) measures adult attachment within romantic relationships in past and present in 36 items, consisting of two subscales of 18 items each (attachment anxiety and attachment avoidance). Each item is rated from 'strongly disagree' (1) to 'strongly agree' (7). The ECR-R is currently the most commonly used and recommended self-report measures with good psychometric properties (Conradi et al., 2006; Sibley et al., 2005; Sibley & Liu, 2004). Cronbach's alpha was 0.88 for attachment avoidance and 0.86 for attachment anxiety. In a validation study of the Dutch version, factor structure could be replicated, reliability was stable over time and there was good evidence for its construct validity

(Kooiman et al., 2013). Cronbach's alpha was 0.94 for attachment avoidance and 0.92 for attachment anxiety. Test–retest reliability of the avoidance subscale was .82, and .84 for the anxiety subscale (p < 0.1).

# 8.1.2 Secondary study parameters/endpoints (if applicable)

Not applicable

# 8.1.3 Other study parameters (if applicable)

Not applicable

# 8.2 Randomisation, blinding and treatment allocation

Not applicable

# 8.3 Study procedures

The procedure begins with a screening on inclusion- and exclusion criteria. Written informed consent is obtained. Participants are asked to complete three online questionnaires (SRS-A, ASQ and ECR-R), by computer each taking no more than 15 minutes to complete.

# 8.4 Withdrawal of individual subjects

Participants' requests for withdrawal will be granted without repercussions.

#### 8.5 Replacement of individual subjects after withdrawal

Not applicable

# 8.6 Follow-up of subjects withdrawn from treatment

Not applicable

# 8.7 Premature termination of the study

The study will be prematurely terminated only when the principal investigator is no longer able to perform principal investigator's duties, and no replacement can be found.

#### 9. SAFETY REPORTING

# 9.1 Temporary halt for reasons of subject safety

In accordance to section 10, subsection 4, of the WMO, the sponsor will suspend the study if there is sufficient ground that continuation of the study will jeopardise subject health or safety. The sponsor will notify the accredited METC without undue delay of a temporary halt including the reason for such an action. The study will be suspended pending a further positive decision by the accredited METC. The investigator will take care that all subjects are kept informed.

# 9.2 AEs, SAEs and SUSARs

# 9.2.1 Adverse events (AEs)

Adverse events are defined as any undesirable experience occurring to a subject during the study, whether or not considered related to [the investigational product / trial procedure/ the experimental intervention]. All adverse events reported spontaneously by the subject or observed by the investigator or his staff will be recorded

# 9.2.2 Serious adverse events (SAEs)

A serious adverse event is any untoward medical occurrence or effect that

- results in death;
- is life threatening (at the time of the event);
- requires hospitalisation or prolongation of existing inpatients' hospitalisation;
- results in persistent or significant disability or incapacity;
- is a congenital anomaly or birth defect; or
- any other important medical event that did not result in any of the outcomes listed above due to medical or surgical intervention but could have been based upon appropriate judgement by the investigator.

An elective hospital admission will not be considered as a serious adverse event.

If an adverse event might occur, the sponsor will be notified. Due to the nature of our research (questionnaires, online at home) we do not expect these kind of SAE's.

The investigator will report all SAEs to the sponsor without undue delay after obtaining knowledge of the events, except for the following SAEs: none .

The sponsor will report the SAEs through the web portal *ToetsingOnline* to the accredited METC that approved the protocol, within 7 days of first knowledge for SAEs that result in death or are life threatening followed by a period of maximum of 8 days to complete the initial preliminary report. All other SAEs will be reported within a period of maximum 15 days after the sponsor has first knowledge of the serious adverse events.

# 9.2.3 Suspected unexpected serious adverse reactions (SUSARs)

Not applicable.

# 9.3 Annual safety report

Not applicable

# 9.4 Follow-up of adverse events

All AEs will be followed until they have abated, or until a stable situation has been reached. Depending on the event, follow up may require additional tests or medical procedures as indicated, and/or referral to the general physician or a medical specialist. SAEs need to be reported till end of study within the Netherlands, as defined in the protocol

#### 9.5 Safety Committee

Ethical approval will be obtained from an institutional review board (CWO Parnassia Psychiatric Institute Academy – Rotterdam – The Netherlands) and Medical Research Ethics Committee Amsterdam UMC.

#### 10. STATISTICAL ANALYSIS

# 10.1 Primary study parameter(s)

Statistical analyses were performed using Statistical Package for the Social Sciences version 27 (SPSS Version 27, IBM, New York, NY, USA). First descriptive statistics were used to analyze participants' demographic data.

Spearman correlation coefficients were used to calculate the correlations between SRS-A scores and ASQ scores, and between SRS-A scores and ECR-R scores.

Multiple regression was used to test whether level of education and having a relationship influence a SRS-A score and attachment and whether this is a positive or a negative effect. For the analyses p-value of < .05 was considered statistically significant.

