#### 1. INTRODUCTION AND RATIONALE

Autism spectrum disorder (ASD) is a neurodevelopmental disorder with early onset, and typical characteristics throughout one's lifetime. It is called a spectrum disorder because of variety in phenotypic presentation and severity of symptoms (Lai et al., 2013). Kanner (1943) described ASD as an inability to form effective contact with others. In the late 1970s, lack of attachment was mentioned as one of the characteristics of ASD (Rutter, 1978). DSM-III American Psychiatric Association, 1980) described ASD as a failure to develop normal attachment behaviour. However, recent research indicates that individuals with ADS are able to form secure attachment, albeit at lower rates and with more challenges (Chandler & Dissanayake, 2014; Giannotti & de Falco, 2021; Rutgers et al., 2004; Teague et al., 2017). In DSM-5-TR (American Psychiatric Association, 2022). Core features are persistent deficits in social communication, social interaction, and restricted, repetitive patterns of behaviour, interests, or activities. The social disability is multifaceted with deficits in social-emotional reciprocity, social non-verbal communication, and developing, understanding, and maintaining relationships. Both ASD and insecure attachment affect social functioning and relationships and little is known about attachment in adults with ASD and the relationship between ASD and attachment in adults.

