#### 4.2 Inclusion criteria

Inclusion criteria are: a DSM-5 ASD diagnosis, age 18-65 years and no intellectual disability (IQ >80).

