#### 11.6 Incentives (if applicable)

#### 12. ADMINISTRATIVE ASPECTS, MONITORING AND PUBLICATION

# 12.1 Handling and storage of data and documents

Researchmanager Data Management (RDM) is used for data collection (scores on questionnaires) and coding and saving data.

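### Does leaving level of education and relationship status undefined in Section 10.1 undermine the regression, above all for the ECR-R?

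*Combined protocol and SAP*

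**What the plan says.** Section 10.1 plans Spearman correlations of the SRS-A with the ASQ and ECR-R scores and then adds: "Multiple regression was used to test whether level of education and having a relationship influence a SRS-A score and attachment". The same sentence goes on to ask for a direction, namely "whether this is a positive or a negative effect". Section 2 names the same two characteristics as correlates of attachment. Neither place gives categories, coding, a time frame or a source.

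Other sections give little help. Section 8.1.3 lists no further study parameters. Section 8.3 says only "Participants are asked to complete three online questionnaires (SRS-A, ASQ and ECR-R"). Section 12.1 names a system that "is used for data collection (scores on questionnaires) and coding and saving data". The one sign that other items are collected is the mention of demographic data in Section 10.1.

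On the ECR-R, Section 8.1.1 says that it "measures adult attachment within romantic relationships in past and present in 36 items". Section 4.2 reads "Inclusion criteria are: a DSM-5 ASD diagnosis, age 18-65 years and no intellectual disability"; neither it nor Section 4.3 sets a condition on relationship history. Section 1 counts difficulty in "developing, understanding, and maintaining relationships" among the social deficits of ASD.

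**The concern.** Two analysts could build different models from this text.

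**Relationship status.** If the item is a present yes/no, the 'no' group holds former partners, who have a romantic relationship to rate, and never-partnered people, who have none. For the two ECR-R subscales the coefficient would then blend two contrasts in unknown shares. A significant result might reflect only that never-partnered people answer a scale about partners differently, and a real gap between current and former partners might be diluted. If only yes/no were recorded, the questionnaire scores could not recover the split. The ASQ is not described as romantic, so it is less exposed.

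**Education.** The plan asks for the sign of an effect. Nominal coding gives several coefficients, possibly of mixed sign.

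There are also smaller mismatches. Section 2 speaks of correlations where Section 10.1 uses regression. The SRS-A as a regression outcome matches nothing in Section 2. Causal wording sits oddly with a cross-sectional design.

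**Working it through.** **The plan's own figures.** There is none for the regression. Section 4.4 sizes the study for a correlation only (56 required, 60 planned), so it cannot settle this point. From the documents come n = 60 and alpha = .05. Every share and effect size below is an assumption.

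**Step 1: what yes/no coding estimates.** Let w be the never-partnered share of those without a partner. For group means:

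coefficient = (1 − w) × (current − past) + w × (current − never)

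With 24 current partners, 36 people have none. With 6, 12 or 18 never partnered, w = 6/36, 12/36 or 18/36, that is 17, 33 or 50%. If current and past partners are equal and never-partnered people score .8 SD higher, the coefficient is −.8w = −.13, −.27 or −.40. Simulation with education independent of status gave the same values.

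The formula holds for raw means, or when education is unrelated to status. If never-partnered people average two levels lower on a five-level education scale (w = 50%, .8 SD), the adjusted coefficient is −.21, not −.40.

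**Step 2: rejection rates.** n = 60, outcome SD 1, education as an independent five-level covariate, two-sided .05. The first four rows use 20,000 runs per setting and the last 4,000. Entries are for 6/12/18 never partnered.

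| Assumed pattern | Yes/no | Current versus past (three-level model) |
|---|---|---|
| Only never-partnered differ, .2 SD | 5.0/5.7/6.6% | about 5% |
| Only never-partnered differ, .8 SD | 7.1/15.0/28.5% | about 5% |
| Only past partners differ, .8 SD | 68/48/28% | 82/77/70% |
| Past and never both differ, .8 SD | about 84% | 81/77/71% |
| Graded: past .4 SD, never .8 SD | 40/48/61% | 29/26/24% |

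**Step 3: reading the table.** In the first two rows the yes/no rejections are not false positives. If never-partnered people score differently, people with and without a partner do differ on average, and that is what Section 10.1 asks about. The 5% in the other column answers a different question, whose true answer in those rows is zero. The third row favours three levels. The fourth and fifth favour yes/no, and in the graded case with 18 never partnered the power of the current-versus-past contrast is less than half (24 against 61%).

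**Step 4: education.** With 3/4/5/6 equal-sized levels and a true correlation of .3, one ordered term has 65–66% power and nominal coding 54/47.5/42/37.5%. The two disagree on significance in 16/23/27.5/33% of datasets. But nothing in the plan suggests nominal coding. A level is ordered, Section 2 plans correlations with it, and Section 10.1 wants a sign. Only one ordered term meets all three.

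**Step 5: is the list of collected items complete?** Section 8.3 does not mention age either, although Section 4.2 needs it. The section is therefore not a full inventory, and its silence on education and relationship status does not show that they go uncollected.

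**The case for a change.** The strongest argument is that relationship status can be read in two ways, current or ever, and that this matters. With assumed shares of 40/30/30% current/former/never and only never-partnered people differing (.8 SD), power is .27 with current yes/no and .79 with ever yes/no. If former and never-partnered people both differ from current partners, the order reverses: .84 against .33. If only former partners differ, the coefficient changes sign (−.40 against +.35). Across four assumed mixes of shares, the two codings disagreed on significance in 26 to 98% of datasets when groups differed.

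The unwritten definition also leaves room for choice. With no true effect each coding keeps about 5% error, but at 40/30/30% they disagree in 8.5% of datasets. An analyst who tried both and reported the better one would reject in (5.4 + 5.1 + 8.5)/2 = 9.5%.

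What stands: the definition can change an ECR-R coefficient, and three recorded levels can be collapsed to two but not the reverse. The documents also do not say how a never-partnered person answers the ECR-R.

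What does not stand is that the plan is wrong as written. The present-tense wording favours current partner yes/no, and a request for one signed effect fits it. Under a graded pattern at 40/30/30% the current, ever and three-level codings have almost the same power (.57, .58, .58). With 6 never-partnered participants and only that group differing, rejection stays between 5.0% and 7.1% for differences of .2 to .8 SD. Whether a never-partnered person's score is comparable depends on the instrument's instructions, which the documents do not reproduce.

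**Conclusion.** No change to the plan is needed. Section 10.1 leaves out a definition that an analyst can fill sensibly from its own wording: partner now or not, and education as one ordered term. That comparison validly answers the question posed, and the Spearman analysis of the SRS-A against attachment does not depend on it.

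The one alternative that would alter a result is to report current against past partners only for the ECR-R. It replaces the plan's question with another. Under the assumptions shown, with 18 never partnered, it gains power in one pattern (70 against 28%) and loses it in two (71 against about 84%, and 24 against 61%). The documents give no shares or effects to decide between them, so it is a trade-off rather than a correction. It would also use one more degree of freedom: at n = 60 and an assumed f² of .15, a two-level status term has power .84 and a joint test of a three-level term .75.

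The rest is wording. Causal terms in a cross-sectional study, correlation in Section 2 beside regression in Section 10.1, and the SRS-A as an unannounced outcome call for care when the results are reported, but they alter none of the numbers. The aim is exploratory by Section 2, so these coefficients will be read as descriptive associations.

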Secure attachments appear to act as a protective factor in the social and cognitive development of children with ASD (Teague, 2017). When demonstrating secure attachment, children with ASD show more complex play behaviours (Naber et al., 2008), more joint attention (Naber et al., 2007), improved social skills and educational opportunities and outcomes (Bauminger et al., 2010. These findings are consistent with observations from the typically developing literature and with predictions from attachment theory (Teague, 2017). The severity of ASD and developmental delay are both associated with less secure attachments (Naber et al., 2006), but there is a lack of consensus on the extent to which attachment insecurity is a function of either developmental delay or the severity of autism symptoms. To the best of our knowledge, research on attachment in adults with ASD is scarce. To date, only one study on attachment in adults with high functioning ASD (*N*=20) found a minority (15%) to be securely attached comparable with a general clinical sample and lower than non-clinical samples, and attachment security was found not to be related to ASD characteristic and IQ (Taylor et al., 2008).

Very little research has investigated the relationship between attachment and behaviour and emotional problems in children with ASD (Teague et al., 2017). The aim of this study is to explore attachment styles in adults with ASD and examining the relationship between attachment and ASD. For individuals with ASD, the principal psychological benefit of knowing their attachment style may be that in those with insecure attachment this knowledge may function as a means of treatment.

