# 4.4 Sample size calculation

A priori power analysis was conducted using G\*Power version 3.1.9.7 (Faul et al., 2007) to determine the minimum sample size required to test the relationship between ASD (SRS-A score) and attachment (ASQ and ECR-R scores). To examine the relationship between SRS-A and attachment, Spearman correlation coefficients are computed. Sample size for Spearman correlation was determined using power analysis in G\*Power version 3.1.9.7 (Faul et al., 2007), using an alpha of 0.05, a power of 0.80, and an effect size of .5 for a two-tailed test. Because Spearman's rank correlation coefficient is computationally identical, power analysis was conducted using software for estimating power of a Pearson's correlation. Based on the aforementioned assumptions, the required sample size was determined to be 56. To prevent the hypotheses from being underpowered, we included a total of 60 participants for each hypothesis.

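### The regressions in section 10.1 leave out age, which is known for every participant and plausibly varies with both education and relationship status, yet their coefficients are to be read as influence

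*Combined protocol and SAP*

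**What the plan says.** Section 10.1 plans three things: descriptive statistics of demographic data, Spearman correlations of SRS-A with ASQ and with ECR-R, and a regression. On the last it says "Multiple regression was used to test whether level of education and having a relationship influence a SRS-A score and attachment", and it adds that the direction of the effect is to be determined. No other predictor is named. Sections 10.2 and 10.3 add no analyses, and no partial correlation or sensitivity analysis is planned anywhere.

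The inclusion criteria (section 4.2) require "a DSM-5 ASD diagnosis, age 18-65 years and no intellectual disability (IQ >80", and section 8.3 begins with screening on those criteria. Age is therefore known for everyone. For IQ, sections 4.2 and 4.3 set only a threshold. No section names an IQ test or says that a score is recorded.

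The objective in section 2 is descriptive: to explore the relationship between ASD and attachment and to calculate correlations.

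**The concern.** Level of education and having a relationship both tend to accumulate over adult life. In a sample that may span 18 to 65 years, either variable can stand in for age. If attachment or SRS-A scores also differ by age, the two coefficients in section 10.1 absorb part of that difference. The plan then reads them as influence, with a sign, and has no analysis that would show whether age is the source.

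Age is a safe covariate here. It cannot be a consequence of attachment or of SRS-A, so adjusting for it does not remove part of the relationship being studied. What is at stake is a published statement that education or partnership affects attachment when the data may only show that younger and older participants score differently.

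**Working it through.** **Plan's own figure.** Section 4.4 states "using an alpha of 0.05, a power of 0.80, and an effect size of .5 for a two-tailed test" and reports that "the required sample size was determined to be 56". By the Fisher z formula, N = ((1.960 + 0.842)/atanh(0.5))² + 3 = (2.802/0.5493)² + 3 ≈ 29.01, rounded up to 30. The stated 56 does not follow from these inputs. That is a separate matter. The checks below use the planned n = 60 (section 4.4: "we included a total of 60 participants for each hypothesis").

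**Inputs.** n = 60 and two-sided alpha .05 come from the documents. All correlations with age, and 40% of participants in a relationship, are assumptions.

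**First-order check, one predictor.** If education has no association of its own, its expected correlation with attachment is the product of the two age correlations. The rejection probability is Φ(d − 1.96) + Φ(−d − 1.96), with d = atanh(r)·√57.
- .2 × .2 = .04: d = 0.302, rejection 6.1%.
- .3 × .3 = .09: rejection 10.5%.
- .4 × .4 = .16: d = 0.1614 × 7.550 = 1.218, rejection 23.0%.

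**Simulation of the planned regression.** Each setting used 20,000 data sets with normal variables and an outcome that depends on age only. Attachment was regressed on education and relationship. The Monte Carlo standard error is √(.05 × .95/20,000) ≈ 0.15 points near 5% and about 0.3 points near 21%.

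| age–education | age–relationship | age–attachment | education significant |
|---|---|---|---|
| .3 | .3 | −.1 | 5.3% |
| .2 | .2 | −.2 | 5.9% |
| .3 | .3 | −.2 | 7.0% |
| .3 | .3 | −.3 | 9.8% |
| .3 | .3 | −.4 | 13.3% |
| .4 | .3 | −.3 | 13.6% |
| .4 | .3 | −.4 | 21.1% |

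At least one of the two predictors is significant in about 11% of studies with all age correlations at .2, and in 16.8% to 28.7% in the last four rows. The comparator is not 5%. Two independent tests give 1 − .95² = 9.75%, and the simulation without confounding gives about 9.5%. The excess is therefore about 1.5 to 19 points. With age in the model, each predictor is significant in 4.7% to 5.4%. These rates apply per outcome scale.

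**SRS-A–attachment correlations.** At n = 60 the critical |r| is .254. For age alone to give an expected correlation of that size, it must correlate √.254 ≈ .50 with both scores. To give the planned .5 it must correlate √.5 ≈ .71 with both. An observed r of .5, adjusted for a variable correlated a with both scores, becomes (.5 − a²)/(1 − a²): .451 for a = .3 and .405 for a = .4.

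**Cost of adjusting.** For a correlation adjusted for one covariate, √(n − 3) becomes √(n − 4). The r detectable with 80% power moves from .355 to .358, and power at r = .5 from 98.6% to 98.4%. For a one-degree-of-freedom regression test with an assumed f² = .15, power is 83.9% with two predictors and 83.8% with four.

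**The case against.** **The link from age to the outcomes is assumed.** No section says that age is related to attachment or SRS-A, and the education categories and age distribution are not given. This stands. With weak links the harm is negligible (5.3% to 7.0% in the first three rows), so the case is one of exposure, not of demonstrated bias. The simulation also takes age as linear. If its relation to education is mainly a threshold among the youngest, a linear term may not remove all of it.

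**The documents do use the demographic data.** A reader might infer that age enters no analysis at all. Section 10.1 summarises demographic data without listing the variables, and age may well be among them. The gap is confined to the association analyses.

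**The unadjusted correlations answer the stated objective.** A reader might infer that confounded SRS-A–attachment correlations would be false positives, or could arise from age or IQ alone. The documents do not support this. Section 2 asks for the marginal correlations, and a marginal correlation produced by a third variable is a real one. Age alone would also need correlations of about .5 with both scores to bring the expected value to significance. Moderate links would distort these correlations more than create them.

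**IQ is weaker ground than age.** A reader might infer that IQ is equally at hand. Only a threshold is required. Section 1 does say that it is unsettled whether "attachment insecurity is a function of either developmental delay or the severity of autism symptoms", but that passage concerns children. The one adult study it cites found attachment security unrelated to IQ. With N = 20 that is weak evidence, but it does not point towards IQ as a confounder.

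**Conclusion.** The point holds for the regressions. Section 10.1 names two predictors that plausibly vary with age, omits age although screening establishes it, and treats the coefficients as influence. Under the assumed range (.2 to .4 in absolute value for education and attachment, .2 to .3 for relationship status, 40% in a relationship, n = 60), education is significant in about 6% to 21% of studies against 5%, and either predictor in about 11% to 29% against about 9.5%. None of these correlations comes from the documents, and at the low end the effect is close to nil. The recommendation rests on the near-zero cost of adjustment and on the wording of section 10.1, not on proof that age distorts the result. It does not extend to replacing the unadjusted Spearman correlations, and for IQ it is conditional on scores being available.

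**What to change.** - Carry age in years from the screening record into the analysis data set and include it as a covariate in every regression in section 10.1. A plot of each outcome against age would show whether a linear term is adequate.
- Replace the language of influence and effect in section 10.1 with association.
- Keep the unadjusted Spearman correlations as the primary answer to section 2, and report age-adjusted partial Spearman correlations beside them as a sensitivity analysis.
- If numeric IQ scores prove to be on file, add an age- and IQ-adjusted version as an optional further sensitivity analysis, stating how many participants have a score and from which tests.

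The cost is SAP wording, one degree of freedom out of 60 and slightly more analysis work. Age needs no new measurement. The optional IQ analysis depends on data that the plan does not say it holds, and scores may be missing or come from different tests.
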